3 STUDY DESIGN

3.1 Overview of Study Design

This will be a double-blinded, placebo controlled randomized clinical trial to evaluate the efficacy of NCG in the treatment of two organic acidemias (severe PA and MMA), and two urea-cycle disorders (late-onset CPSD and OTCD). Figure 3 summarizes the design of the proposed trial.

Figure 3. Study Overview Diagram

Protocol Overview

- Eligibility** – Briefly, subjects (a) aged >1 week with verified diagnosis of CPSD or OTCD or (b) subjects of any age with verified diagnosis of PA or MMA and ammonia level \geq 70mcmol/L. All subjects (or a first-degree relative) must have had a recorded plasma ammonia \geq 100 mcmol/L and must have presented initially at >1 week of age for CPSD or OTCD. Subjects must not be pregnant. A complete listing of eligibility criteria is included in Section 4 (Study Population).
- Enrollment** – Informed consent from the participant or one parent or legal guardian.
- Randomization** – At each hyperammonemic episode, participants will be randomized to either placebo plus standard therapy (PLBO-STD) or NCG plus standard therapy (NCG-STD) at a dose of 150 mg/kg/ day or 3.3 g/m²/day for patients >15 kg, divided into 2 equal doses and administered enterally by nasogastric or gastrostomy tube or by oral syringe.
- Study Treatment** – The NCG/PLBO dose will be administered for metabolic decompensation for 7 days or until discharge, whichever is shorter.
- Concomitant Standard Treatment** – Participants will continue receiving standard treatment which may include intravenous glucose (and insulin if required), L-carnitine dosing and/or dialysis. Ammonia scavengers may only be administered in patients with urea cycle disorders.

- **Laboratory Measurements** – Plasma ammonia testing should be performed as clinically indicated, including checking the level at admission and at least every 6-12 hours for the first 48 hours and every day thereafter if the previous level was ≥ 50 $\mu\text{mol/L}$, for a total of 7 days or until discharge, whichever is shorter. Plasma amino acids should also be checked as clinically indicated at admission and at least every 2 days thereafter, if ammonia levels are measured. Safety laboratory assessments including complete blood cell count, liver and kidney function tests, amylase and lipase testing, as well as a coagulation profile (if clinically indicated) will be done at the time of initial admission, at 3-5 days, at 6-7 days or at discharge, whichever is shorter.
- **Electrocardiogram (EKG) Test** – At each episode, participants will have an EKG at admission and repeated on day 3-5 of treatment (48 hours following the initial drug administration, before discharge if earlier) to check for cardiac toxicity.
- **Functional Scale Score (FSS)** – Determined for each episode at admission and every day of hospitalization for a total of 7 days or until discharge, whichever is shorter.
- **Recurrent Episodes** – Each subsequent admission for metabolic decompensation will follow the same above procedure but has to occur at least 7 days after the last discharge to guarantee study drug wash out before the next administration should patient have received study drug.

4 STUDY POPULATION

Patients enrolled in the long-term outcomes study being conducted in parallel are eligible to enroll in this study when the long-term outcomes study closes, provided that all other inclusion and exclusion criteria are satisfied.

4.1 Inclusion Criteria

- Aged older than 1 week with an established diagnosis of CPSD or OTCD (as follows):
 - Diagnosed with late-onset CPSD confirmed by detection of pathogenic mutation(s), and/or decreased (<20% of control) CPS enzyme activity in liver **OR**
 - Diagnosed with late-onset OTCD by detection of pathogenic OTC mutation, OR decreased (<20% of control) OTC enzyme activity in liver OR elevated urinary orotate (greater than 20 μ M/mM) following allopurinol loading with absence of argininosuccinic acid
 - **AND:** Subject or subject's first-degree relative had plasma ammonia level ≥ 100 mcmol/L > 1 week of age

OR

- An established diagnosis of PA or MMA (as follows):
 - Diagnosed with PA by semi-quantitative urine organic acid analysis, defined as presence of elevated methylcitric acid and normal methylmalonic acid levels and no evidence of biotin-related disorders in the organic acid analysis **OR**
 - Diagnosed with MMA by semi-quantitative urine organic acid analysis, defined as elevation of methylmalonic acid and no evidence of vitamin B12 dependent disorder on plasma amino acid analysis (B12 dependency is defined by documented B12 responsiveness)
 - **AND:** Subject or subject's first-degree relative had plasma ammonia level at any time ≥ 100 mcmol/L
- Able to receive medications orally, by nasogastric (NG)-tube or by gastric (G)-tube
- No concomitant illness which would preclude safe participation as judged by the investigator
- If post-menarcheal must have a negative pregnancy test prior to administration of study drug at each episode
- Signed informed consent by the subject or the subject's legally acceptable representative

4.2 Exclusion Criteria

- Administration of NCG within 7 days of participation in the study
- Use of any other investigational drug, biologic, or therapy.
- Planned participation in any other clinical trial
- Diagnosis of any medical condition causing hyperammonemia that is not PA or MMA. CPSD or OTCD. Other urea cycle disorders will be excluded from this study.
- Any clinical or laboratory abnormality or medical condition that, at the discretion of the investigator, may put the subject at an additional risk by participating in this study
- Has had a liver transplant
- Is not expected to be compliant with this study in terms of returning to site for subsequent episodes of hyperammonemia crises
- Is pregnant

5 STUDY PROCEDURES

5.1 Screening of Potential Subjects

Prior to enrollment, patients must be deemed by the site PI, or his assigned surrogate, to meet eligibility criteria.

5.1.1 Confirmation of diagnosis of PA, MMA, CPSD or OTCD

5.1.1.1 Diagnosis of PA or MMA

Results from the subject's urine organic acid analysis, performed via semi-quantitative methods by gas chromatography–mass spectrometry (GCMS), should be reviewed. Patients who do not meet these laboratory diagnostic criteria will not be enrolled.

5.1.1.1.1 Laboratory Diagnostic Criteria for PA

- 1) Elevation of methylcitric acid and propionylglycine
- 2) No elevation in methylmalonic acid
- 3) No evidence of biotin-related disorders

5.1.1.1.2 Laboratory Diagnostic Criteria for MMA

- 1) Elevation of methylmalonic acid
- 2) No elevation of homocysteine, total homocysteine, or homocysteine-cysteine disulfide by plasma amino acid analysis
- 3) No response to 1 mg IM hydroxocobalamin injections

5.1.1.1.3 Laboratory Diagnostic Criteria for CPSD

- Detection of pathogenic CPS1 mutation(s) **OR**
- Decreased (<20% of control) CPS enzyme activity in liver

5.1.1.1.4 Laboratory Diagnostic Criteria for OTCD

- Detection of pathogenic OTC mutation **OR**
- Decreased (<20% of control) OTC enzyme activity in liver **OR**
- Elevated urinary orotate (greater than 20 μ M/mM) following allopurinol loading, with absence of argininosuccinic acid on plasma amino acid analysis

5.1.1.2 Documentation of Hyperammonemia

- 1) The subject (or subject's first-degree relative) should have a previously documented ammonia level at any time of ≥ 100 μ mol/L
- 2) If diagnosed with CPSD or OTCD (as per above), initial hyperammonemia should have occurred > 1 week of age

In some cases, a subject may have been diagnosed prenatally, or before the manifestation of symptoms, because of previously-identified affected family member. As a result, the subject may have been treated prospectively and averted any early hyperammonemic events. In such cases, the previously-identified first-degree relative must meet the above criteria instead.

5.2 Informed Consent Procedures

Participants will be recruited from all participating sites and their metabolic services. Ideally, patients will be recruited to this study during periods of clinical and metabolic stability, rather than at the time of presentation of acute illness or hyperammonemia. Whenever possible, the participants (or

guardians) will be given a copy of the consent form for review, several days before the formal informed consent process takes place.

For participants who can provide informed consent:

The licensed physician investigator will meet with the potential study participant to describe the study. Patients will be brought to a private, quiet room where the benefits and risk of study will be explained thoroughly, and any questions will be answered. The investigator will then give the patient time to read the consent form and consider participation. The investigator will return to answer questions, ensure that the patient understands the information provided, and obtain informed consent.

For participants unable to provide informed consent who arrive with parents/guardians:

The site PI will meet with the parent(s) or guardian(s) to describe the study. Parents will be brought to a private, quiet room where the benefits and risks of the study will be explained thoroughly, and any questions will be answered. The investigator will then give the parent(s) time to read the consent form and consider participation. The investigator will return to answer questions, ensure that the parent/guardian understands the information provided, and obtain informed consent.

For participants unable to provide informed consent arriving without parents/guardians:

Some of these patients may be transferred directly from another institution without parents or guardians. Patients' families will be first contacted by phone by clinical personnel to discuss the possibility of participating in a clinical trial. Should they be interested, informed consent will be obtained by the site PI by telephone before the study can begin. The investigator will speak with the parent/guardian by phone, and provide them with a copy of the consent form (e.g., by fax, e-mail). When the parent/guardian receives the consent form, it will be immediately signed and sent/faxed back to the investigator. No research-related activities will occur until a signed hard copy of the consent form has been received by the investigator.

For participants who are being recruited during a period of clinical and metabolic stability:

Whenever possible, patients will be recruited to participate during periods of clinical and metabolic stability. The site PI will meet with these patients (and their families, if applicable) following their routine clinical visits to discuss study participation, to answer questions, to ensure that all information provided is understood, and to obtain informed consent. Patients who are not scheduled for a routine clinical visit within the next 3 months will be contacted by phone by clinical personnel to discuss the possibility of participating in a clinical trial. Should they be interested, informed consent will be obtained by the site PI by telephone. The investigator will speak with the patient or parent/guardian by phone, and provide them with a copy of the consent form (e.g., by fax, e-mail, or post). When the patient or parent/guardian receives the consent form, it will be signed and returned to the investigator. No research-related activities will occur until a signed hard copy (original or facsimile) of the consent form has been received by the investigator.

Informed consent documents will be available in English. If patients or their parents/guardians are only fluent in another language, and the site has a standard operating procedure for informed consent in that language (such as an on-call interpreter and if available abbreviated consent form in respective language) and the site IRB has approved the process for this study in advance, non-English speaking patients, and parents/guardians will also be included.

5.3 Retention Procedures

Every effort will be made to identify patients who have enrolled in this study at their next presentation to the emergency department or another medical facility.

- At the time of enrollment, patient families will be provided with a card, indicating that they are participating in an investigational drug trial, to be presented to hospital staff at

Short-Term Outcome of NCG in Hyperammonemia

subsequent episodes of illness. They will also be reminded to inform the on-call genetics or metabolism attending physician of their participation in this trial.

- The last note from the treating genetics and/or metabolism physician will indicate in the plan, or in an addendum, that the patient is participating in a clinical investigational drug trial
- The patient charts will be flagged, if possible, indicating that the patient is participating in a clinical investigational drug trial

5.4 Duration of Study and Visit Schedule

5.4.1 Hyperammonemia Episodes

At any time after the initial enrollment, participants may present to the hospital with PA-, MMA-, CPSD- or OTCD- associated symptoms (see Sections 1.1.2-1.1.5). Indicated clinically, the plasma ammonia level should be verified.

- Subjects are not eligible to receive study drug if they have received NCG or study drug any time in the preceding 7 days.
- If plasma ammonia is ≥ 70 $\mu\text{mol/L}$ at presentation (confirmed on site) or during a hospitalization for an acute decompensation, participants should receive the study drug. The time from an episode- qualifying ammonia level to randomization should not be longer than a maximum of 4 hours.

5.4.1.1 Random Group Assignment

At each hyperammonemia episode, subjects will be randomized to a treatment arm. Randomization will be performed online using a stored, pre-generated, encrypted randomization schedule created by the CNMC Division of Biostatistics and Study Methodology. To complete the process, the Site Pharmacy will simultaneously receive an automated notification of the assignment to enable them to prepare the correct prescription for the participant. The time from randomization to study treatment administration should be as brief as possible and no longer than a maximum of 6 hours.

5.4.1.2 Concurrent with Randomization

Pre-Treatment

1. Indicated clinically, a blood sample will be drawn for plasma ammonia and amino acid analysis. All patients are expected to have clinically indicated vascular access. If vascular access is inadequate, blood will be drawn by venipuncture. All ammonia levels measured up to 24 hours prior to first treatment administration will be recorded. Ammonia levels measured >24 hours prior to first treatment administration will not be recorded in this study.
2. Laboratory safety assessments: complete blood count (CBC), liver function tests (LFT), renal function test (RFT), amylase and lipase. If indicated clinically, a coagulation profile (PTT and INR) should also be done. A pregnancy test is required (if applicable).
3. Electrocardiogram (EKG) test
4. Functional Status Scale (FSS) assessment

Table 1. Hospitalization Study Procedures

Short-Term Outcome of NCG in Hyperammonemia

| | Day 1 | | | | | Day 2 | | Day 3 | | Day 4 | | Day 5 | | Day 6 | | Day 7 | | Day 30 (≤6 Months) |
|--|-------|---------------|---|----|----------------|-------|----|-------|----|----------------|----|----------------|-----|----------------|-----|----------------|-----|-----------------------|
| Time (hours) | 0 | Post Dialysis | 6 | 12 | 18 | 24 | 36 | 48 | 60 | 72 | 84 | 96 | 108 | 120 | 132 | 144 | 156 | |
| Confirm Eligibility | X | | | | | | | | | | | | | | | | | |
| Pregnancy Test^b | X | | | | | | | | | | | | | | | | | |
| Randomization | X | | | | | | | | | | | | | | | | | |
| Plasma Ammonia Level^c | X | (X) | X | X | X ^d | X | X | X | | X ^f | | X ^f | | X ^f | | X ^f | | |
| Plasma Amino Acids^c | X | (X) | | | | X | | | | X ^g | | | | X ^g | | | | |
| Safety Labs^c | X | | | | | | | | | X ^h | | | | X | | | | |
| EKG Testⁱ | X | | | | | | | | | X ⁱ | | | | | | | | |
| Functional Status Scale^c | X | | | | | X | | X | | X | | X | | X | | X | | X |
| Concomitant Medications Log | | | | | | X | | X | | X | | X | | X | | X | | X |
| Adverse Events Log | | | | | | X | | X | | X | | X | | X | | X | | X |
| Study Drug (NCG or PLBO) | X | | | | X | X | X | X | X | X | X | X | X | X | X | X | X | |
| Treatment Administration Log | X | | | | X | X | X | X | X | X | X | X | X | X | X | X | X | |
| Blood Transfusion Log | X | | | | X | X | X | X | X | X | X | X | X | X | X | X | X | |

NCG=N-carbamylglutamate; PLBO=Placebo

^a Suggested timeline to be followed for 7 days, or until discharge if discharged prior to 7 days of drug administration

^b For women of childbearing potential only. A serum pregnancy test will be performed in the event of a positive or equivocal urine pregnancy test result, or if the patient is anuric

^c Allowable windows for day 3 (days 3-5) and day 7 (days 6-7), unless otherwise indicated

^d Plasma ammonia should be drawn as frequently as clinically indicated, for example, every 6 hours during the first 24-hour window if the patient has a central or peripheral venous catheter.

^e Only to be drawn if dialysis is performed. Blood draws should be performed immediately upon termination of hemodialysis or hemofiltration, even if the regular time-point labs have been drawn.

^f Plasma ammonia should be drawn as frequently as clinically indicated, for example, after 48 hours, follow-up ammonia should be obtained if the prior measurement was ≥ 50 μ mol/L

^g Amino acids should be drawn as frequently as clinically indicated, for example, obtained only if ammonia also obtained (see f)

^h Safety Lab blood draw to be obtained on day 6-7, or if discharged <7d, within 24h prior to discharge

ⁱ EKG should be done before treatment begins and repeated once between Days 3-5 or before discharge

5.4.1.3 Post-Randomization

Day 1

Short-Term Outcome of NCG in Hyperammonemia

1. As per their assignment, the participant will be started on NCG (150 mg/kg/day for patients ≤15 kg or 3.3 g/m²/day for patients >15 kg in two divided doses) OR PLBO (three-quarters tablet/kg/d for patients ≤15 kg or 16.5 tablets/m²/day for patients >15 kg, in two divided doses) to be administered through a nasogastric tube, or if not available, by oral syringe, as described in Section 6.1. The participant will also continue to receive standard therapy.
2. Following the first drug administration, the subsequent drug administration should be given between 6 and 12 hours after the first dose, at a standard drug administration time for the site. All subsequent doses should be given every 12 hours.
3. Indicated clinically, plasma ammonia testing will be performed every 6 hours following study drug administration if the patient has a central or peripheral catheter. In all other cases, plasma ammonia testing will be performed every 12 hours, as indicated clinically.
4. Clinical monitoring FSS
5. Treatment administration log, concomitant medications log, blood transfusion log, and adverse events log will be completed daily

Day 2

1. NCG/PLBO Rx. & Standard Rx every 12 hours.
2. Plasma ammonia every 12 hours (as indicated clinically)
3. Amino acids (as indicated clinically)
4. Clinical monitoring FSS
5. Treatment administration log, concomitant medications log, blood transfusion log, and adverse events log will be completed daily

Day 3 (if not yet discharged)

1. NCG/PLBO Rx. & Standard Rx every 12 hours.
2. Plasma ammonia (as indicated clinically)
3. Safety labs should be performed between days 3 - 5
4. EKG test should be performed between days 3-5
5. Clinical monitoring FSS
6. Treatment administration log, concomitant medications log, blood transfusion log, and adverse events log will be completed daily

Day 4 (if not yet discharged)

1. NCG/PLBO Rx. & Standard Rx every 12 hours.
2. Plasma ammonia (as indicated clinically)
3. Amino acids (as indicated clinically)
4. Clinical monitoring FSS
5. Treatment administration log, concomitant medications log, blood transfusion log, and adverse events log will be completed daily

Day 5 (if not yet discharged)

1. NCG/PLBO Rx. & Standard Rx every 12 hours.
2. Plasma ammonia (as indicated clinically)
3. Clinical monitoring FSS
4. Treatment administration log, concomitant medications log, blood transfusion log, and adverse events log will be completed daily

Day 6 (if not yet discharged)

Short-Term Outcome of NCG in Hyperammonemia

1. NCG/PLBO Rx. & Standard Rx every 12 hours.
2. Plasma ammonia (as indicated clinically)
3. Safety labs should be performed between days 6 – 7
4. EKG test should be performed between days 6-7 (if not done already between days 3-5)
5. Amino acids (as indicated clinically)
6. Clinical monitoring FSS
7. Treatment administration log, concomitant medications log, blood transfusion log, and adverse events log will be completed daily

Day 7 (if not yet discharged)

1. NCG/PLBO Rx. & Standard Rx.
2. Plasma ammonia (as indicated clinically)
3. Safety labs if not done on Day 6
4. EKG if not already done
5. Clinical monitoring FSS
6. Treatment administration log, concomitant medications log, blood transfusion log, and adverse events log will be completed daily

Day 8 (if not yet discharged)

1. The final dose of NCG/PLBO Rx. & Standard Rx.
2. Plasma ammonia (as indicated clinically)
3. Treatment administration log, concomitant medications log, blood transfusions log and adverse events log will be completed a final time.

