1.3.2.2 Carbaglu in Secondary Deficiencies of NAG

Several publications have pointed out the potential of NCG as a therapeutic adjunct to the treatment of hyperammonemia in secondary deficiencies of NAG (i.e., not resulting from NAGS deficiency). All these reports were uncontrolled case reports or case series^{10-13,15,20}.

Our first project was initially funded for 34 months from 8/5/2008 through 5/31/2011. The original specific aims were: 1) To determine whether 3-day treatment with NCG improves or restores ureagenesis in patients with NAGS deficiency, Carbamyl phosphate synthase (CPSD), PA, MMA and hyperinsulinism and hyperammonemia syndrome (HHS), and 2) To evaluate the safety of short-term (3-day) treatment with NCG. The accomplishments thus far indicate that 3-day treatment with NCG:

- Normalizes ureagenesis rate, plasma ammonia, glutamine and urea in NAGS deficiency^{10,21}
- Enhances ureagenesis and reduces plasma ammonia and glutamine levels in PA⁹
- Improves ureagenesis and decreases plasma ammonia and glutamine in some patients with CPSD
- Improves ureagenesis in some patients with HHS

Short-Term Outcome of NCG in Hyperammonemia

- Is safe at the prescribed dose of 100/mg/k/d or 2.2 g/m²/d

In addition, we found that a single dose of NCG rapidly augments ureagenesis rate in healthy adults⁸.

[figure not shown]

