6 STUDY TREATMENTS

6.1 Study Intervention

Carbaglu® 200 mg Dispersible Tablets (N-carbamylglutamate), scored in three places, allowing each tablet to be broken into four 50 mg pieces.

The target dose is 150 mg/kg/d for patients \leq 15kg or 3.3 g/m²/day for patients $>$ 15kg, divided into two equal doses 12 hours apart. Each dose will be rounded to the nearest 50mg using the dosing nomograms provided. The maximum variance from the calculated target daily dose and the actual daily dose will be 23.5% or less. Study drug will be prepared for administration according to the package insert. The suspension has a slightly acidic taste and a white, cloudy appearance. Participants will either receive PLBO or the study intervention, NCG (Carbaglu®) 150 mg/kg/day for patients \leq 15kg or 3.3 g/m²/day for patients $>$ 15 kg.

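### The day-by-day dosing text permits three half-doses in the first 24 hours and lists a Day 8 dose; the 12-hour interval, the two-dose day and the 7-day course stated elsewhere do not accommodate these

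*Combined protocol and SAP*

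**What the plan says.** **Daily amount and interval.** Section 6.1 gives 150 mg/kg/day up to 15 kg, or 3.3 g/m²/day above 15 kg, "divided into two equal doses 12 hours apart". Item 1 of Day 1 in section 5.4.1.3 also has two doses a day: "the participant will be started on NCG (150 mg/kg/day for patients ≤15 kg or 3.3 g/m²/day for patients >15 kg in two divided doses".

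**Second dose.** Item 2 of the same Day 1 list says "the subsequent drug administration should be given between 6 and 12 hours after the first dose", timed to fit the site's usual dosing hours. It continues: "All subsequent doses should be given every 12 hours".

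**Variance limit.** Section 6.1 has each dose rounded to the nearest 50 mg by a nomogram. The next sentence reads "The maximum variance from the calculated target daily dose and the actual daily dose will be 23.5% or less".

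**Course length.** Section 3.1: "The NCG/PLBO dose will be administered for metabolic decompensation for 7 days or until discharge, whichever is shorter". The note to Table 1 also gives 7 days. Table 1 has no Day 8 column and its last dosing mark is at 156 hours. The day list in section 5.4.1.3 nevertheless has a Day 8 entry: "The final dose of NCG/PLBO Rx. & Standard Rx".

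**Laboratory tests.** Section 5.4.1.3 and the Table 1 notes place the last in-hospital safety tests on days 6–7. Section 2.2 asks for tests just before treatment ends and again from about thirty days after the last dose.

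**The concern.** A pharmacy or ward working from section 6.1 and one working from section 5.4.1.3 can give different amounts of drug to identical patients. The difference falls in the first day, when ammonia is sampled most densely and the primary time-to-event endpoint has just started to run from the first dose. Describing the tested regimen simply as 150 mg/kg/day would then misstate early exposure for every episode with a second dose before 12 hours.

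The end of the course is similarly unclear. Two sites could both believe that they gave the full 7-day course and differ by one or two doses. The last in-hospital safety tests are tied to day numbers rather than to the last dose. Section 9.11 names an incorrect dose as an example of a protocol violation, so a monitor needs one rule against which to judge the treatment log.

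**Working it through.** **Inputs.** Half-dose: 150 / 2 = 75 mg/kg, or 3.3 / 2 = 1.65 g/m² (sections 5.4.1.3 and 6.1). First interval *s*: 6 to 12 hours; later interval: 12 hours (section 5.4.1.3). Tablet strength: 200 mg (section 6.1).

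**Reproducing the stated daily dose.** 2 × 75 = 150 mg/kg and 2 × 1.65 = 3.3 g/m². The placebo counts match: 0.75 tablet × 200 mg = 150 mg per kg, and 16.5 tablets × 200 mg = 3.3 g per m².

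**First 24 hours.** Doses fall at 0, *s*, *s* + 12, *s* + 24 and so on. The third dose is before hour 24 whenever *s* + 12 < 24, that is, whenever *s* < 12.

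| *s* (h) | Dose times before 24 h | Amount | Share of daily dose | Doses before 168 h | First dose at or after 168 h |
|---|---|---|---|---|---|
| 6 | 0, 6, 18 | 225 mg/kg or 4.95 g/m² | 150% | 15 | 16th, at 174 h |
| 8 | 0, 8, 20 | 225 mg/kg or 4.95 g/m² | 150% | 15 | 16th, at 176 h |
| 10 | 0, 10, 22 | 225 mg/kg or 4.95 g/m² | 150% | 15 | 16th, at 178 h |
| 12 | 0, 12 | 150 mg/kg or 3.3 g/m² | 100% | 14 | 15th, at 168 h |

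From hour 24 onward, every 24-hour period contains two doses.

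**Table 1.** As extracted, the study-drug row has 14 marks: 0, 18, 24, 36 and then every 12 hours to 156. The first two gaps are 18 and 6 hours. A second dose at 18 hours fits neither the 6–12 hour window nor a 12-hour interval. The table may have been damaged in extraction, so little weight goes on this.

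**Doses in a full course.** Let Day 1 hold *a* doses, Days 2–6 two each, Day 7 two (keeping the 12-hour rule) and Day 8 one. The total is *a* + 10 + 2 + 1.

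- *a* = 1: 14 doses, 14 × 75 = 1,050 mg/kg.
- *a* = 2: 15 doses, 1,125 mg/kg.
- *a* = 3: 16 doses, 1,200 mg/kg (1,200 / 1,050 = 1.14).

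On calendar days, *a* = 1 when the second dose falls after midnight. The Day 8 dose is then the 14th, at *s* + 144 = 150 to 156 hours, inside 168 hours. On days counted from the first dose, as Table 1's hours run, the Day 8 dose is the 15th (*s* = 12) or the 16th (*s* < 12). The Day 7 entry omits the 12-hour interval. Reading it as one dose lowers each total by one, but leaves more than 12 hours before the Day 8 dose.

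**The 23.5% figure.** At an assumed 1.08 kg, the half-dose is 75 × 1.08 = 81 mg, rounded to 100 mg; the error is 19 / 81 = 23.46%. From 2 kg upward the largest rounding error is about 14%, and from 2.5 kg it is 11.1%. The weights are assumptions, because the nomograms are not in the documents. The figure can therefore arise from rounding alone.

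**The case against.** The strongest reply is that the 6–12 hour window is a deliberate one-off step to bring the patient onto the site's dosing times, after which every 24 hours has two doses. Counted by calendar day, three doses can share a day only if the first is given before 06:00, since the third comes at least 18 hours later. That explains the window. It does not remove the conflict with the 12-hour interval in section 6.1, and no text says that the daily dose is to be counted by calendar day.

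Several stronger readings are tempting, and the documents do not support them:

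- **That three doses are always given.** They are permitted; a second dose at exactly 12 hours gives two.
- **That the 23.5% limit is breached by the extra 50%.** The limit directly follows the rounding rule and most naturally bounds rounding error. Its wording does not confine it to rounding, so its scope is unclear, but a breach is not shown.
- **That the Day 8 dose is necessarily extra, or that the course is 16 doses.** With calendar days and a late first dose it is the 14th. Sixteen is the top of a range.
- **That no safety tests follow the last dose.** Section 2.2 provides for them from about thirty days, although Table 1 as extracted shows no safety-test mark there. Section 5.4.1.4 adds adverse-event follow-up for 72 hours after treatment. Only the in-hospital timing is loose.
- **That the earlier safety statement, "Is safe at the prescribed dose of 100/mg/k/d or 2.2 g/m²/d", is newly exceeded.** The planned 150 mg/kg/day exceeds it on every reading, so it does not separate the schedules.
- **That the comparison is biased.** Placebo follows the same schedule, and section 5.6 has the time and dose of each administration logged, so actual exposure can be recovered.

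It is also fair to say that a site following section 5.4.1.3 is obeying the protocol. Whether a monitor would log a violation cannot be known; the point is that the text supports either judgement.

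**Conclusion.** The contradiction is real and lies in the operative dosing text. For every second dose earlier than 12 hours, section 5.4.1.3 permits 225 mg/kg or 4.95 g/m² in the first 24 hours, 150% of the daily dose that it and section 6.1 state. At exactly 12 hours there is no excess. This counts nominal half-doses before rounding, over 24 hours from the first dose.

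The Day 8 entry has no place in Table 1. Whether it exceeds the 7-day course depends on an undefined day: the total is 14, 15 or 16 doses if 12-hourly dosing is kept through Day 7. The consequence is uncertainty about exposure, safety timing and compliance. The sample size and the between-arm comparison are not affected. It should be corrected.

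**What to change.** Reconcile sections 3.1, 5.4.1.3 and 6.1 and Table 1 so that the same four things are stated everywhere:

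1. The interval between the first and second doses, with the amount of drug in the first 24 hours that follows from it.
2. The last dosing time and the number of doses in a full course.
3. What a day means: a calendar day, or 24 hours from the first dose.
4. Whether the 23.5% limit covers rounding only or all departures from the daily target.

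Then align the in-hospital end-of-treatment safety tests, now on days 6–7, with the reconciled last dose, and check the 18-hour mark in the source copy of Table 1. Which interval and which last dose apply is for the investigators and the sponsor to decide.

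For episodes already treated, the treatment logs allow the number of doses in the first 24 hours and per episode to be reported by arm. The cost is wording, through the written-amendment route of section 9.10. No new data are needed.
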